## 4 Study Objectives and Endpoints

### 4.1 Study Objectives

#### Protocol 1

**Specific Aim 1:** Utilizing a prospective randomized clinical trial study design, we will determine whether heat therapy improves **blood pressure** (both in clinic and ambulatory) better than dynamic aerobic exercise, the gold-standard non-pharmacological treatment of essential HTN. Specifically, we hypothesize that 30 sessions of passive heat therapy using hot water immersion over 8-10 weeks will improve blood pressure in HTN individuals to a greater extent than 30 sessions of exercise training over the same time period.

**Specific Aim 2:** We will determine whether heat therapy will improve biomarkers of arterial health and compare responses to exercise training. We hypothesize that 30 sessions of heat therapy will improve arterial stiffness in HTN to a greater extent than exercise. Furthermore, we hypothesize key clinical biomarkers of systemic inflammation and oxidative stress will be improved following heat therapy.

**Specific Aim 3:** In an exploratory aim, we will determine whether the acute decreases in blood pressure following an initial heat therapy session or exercise peak test predict the sustained reduction in resting blood pressures following heat therapy treatment or exercise training in HTN. These findings would provide significant predictive information beyond baseline resting blood pressures. We hypothesize that the reduction in blood pressure following acute stressors will be predictive of treatment effects on resting blood pressure.

#### Protocol 2

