**HEAT THERAPY VS EXERCISE TRAINING IN HYPERTENSION SAP**

dbp_dipper	Aim 1/Secondary	Categorical; non-dipper <10%, dipper ≥10% to <20%, and extreme dipper ≥20% change in diastolic BP at night calculated from ambulatory BP day and night averages
pwv	Aim 2/Primary	Continuous; average of three pulse wave velocity measurements collected at pre-, interim-, and post-intervention timepoints
il6_lg2	Aim 2/Secondary	Continuous; Biomarker IL-6 with the lower limit of detection (LLD) of 0.031 imputed for <LLD, log2 transformed for normalcy
crp_lg2	Aim 2/Secondary	Continuous; Biomarker CRP with the lower limit of detection (LLD) of 0.031 and upper LD (ULD) of 50 imputed for <LLD and >ULD, log2 transformed for normalcy
et1_lg2	Aim 2/Secondary	Continuous; Biomarker ET-1 with the lower limit of detection (LLD) of 0.031 imputed for <LLD, log2 transformed for normalcy
alb_lg2	Aim 2/Secondary	Continuous; Biomarker urine albumin with the lower limit of detection (LLD) of 0.031 imputed for <LLD, log2 transformed for normalcy
Supine.SBP.low	Aim 3/Primary	Continuous; average of three lowest consecutive supine systolic blood pressure measurements taken every 5 minutes for an hour post-intervention during supine recovery (for Heat Therapy: syst_bp55_ht_s1 to syst_bp110_ht_s1; for Exercise Training: for Heat Therapy: syst_bp55_ex_s1 to syst_bp110_ex_s1)
Supine.DBP.low	Aim 3/Primary	Continuous; average of three lowest consecutive supine systolic blood pressure measurements taken every 5 minutes for an hour post-intervention during supine recovery (for Heat Therapy: syst_bp55_ht_s1 to syst_bp110_ht_s1; for Exercise Training: for Heat Therapy: diast_bp55_ex_s1 to diast_bp110_ex_s1)
Supine.SBP.1.ch	Aim 3/Primary	Change from average pre-session resting SBP to Supine.SBP.low
Supine.DBP.1.ch	Aim 3/Primary	Change from average pre-session resting DBP to Supine.SBP.low
eGFR	Aim 1/Exploratory	eGFR was calculated using the CKD-EPI Creatinine-Cystatin Equation (2021) using the CKDEpi_RF.creat.cys function in the nephron R package and rounded to two decimal places
uacr	Aim 1/Exploratory	Urine albumin creatinine ratio (mg/g) was calculated by dividing urine albumin by urine creatinine/1000 rounded to 2 decimal places
Protocol 2		
cognitive_score	cognitive/Primary	Averaged z-scores (centered & divided by standard deviation) of age-corrected picture sequence score (age_cor_score)

		and age-corrected list-sorting score (list_age_cor_scpre)
--	--	--

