## 9.1 Exploratory Efficacy Analyses

In addition to Protocol 1 primary analyses, additional exploratory analysis will include analyses of covariance (ANCOVA) for each dependent variable of interest, in which pretest values will be entered as a covariate and treatment condition will be specified as a fixed factor in ANCOVA models. Demographic and physiological variables age, sex, and body mass index will be added one at a time to the ANCOVAs to test for an interaction on treatment effects using the following ANCOVA models with pre-intervention systolic or diastolic blood pressure (Pre SBP, Pre DBP) included as a continuous covariate. ANCOVA models based on the formula Interim or Post BP ~ Pre BP + <Interaction variable> + Intervention + <Interaction variable>\*Intervention and included the following terms in addition to Pre BP: Model 2, Pre BP\*Intervention; Model 3, Age + Age\*Intervention; Model 4, Sex + Sex\*Intervention interaction; Model 5, BMI + BMI\*Intervention interaction. SBP, DBP, age and body mass index (BMI) will all included in models as continuous variables with means estimated at selected values of interaction terms to illustrate how blood pressure measures did or did not vary by subgroup.

For Protocol 1 Aim 3, which is an exploratory aim, analyses of covariance (ANCOVA) models will be used to determine the predictive potential of acute responses for chronic changes in blood pressure. To test the association between acute decreases in blood pressure following an initial heat therapy session or exercise peak test and sustained reduction in resting blood pressures as measured by post-intervention ambulatory blood pressure, we will perform ANCOVA models with pre-session systolic or diastolic blood pressure (Pre-session SBP, Pre-session DBP) included as a continuous covariate. Pre-session BP is an average of three pre-session measurements and Post-session BP is lowest

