average of three consecutive readings taken every five minutes in the 55-110 minutes following the hour-long intervention. Group means for ambulatory blood pressure at the post-intervention timepoint will be estimated using the following formulas: Model 1, Post ambulatory BP ~ Pre-session BP + Intervention; Model 2, Post ambulatory BP ~ Pre-session BP + Intervention + Intervention\* Pre-session BP; Model 3, Post ambulatory BP ~ Pre-session BP + Intervention + Post-session BP + Intervention\* Post-session BP. BP measures will be included in models as continuous variables with means estimated at selected values of interaction terms to illustrate how blood pressure measures did or did not vary by subgroup. Additionally, exploratory correlations and PCA were performed among the following Project 1 variables: age, body mass index (BMI), HbA1c, total cholesterol (TC), Interleukin-6 (IL-6), C-reactive Protein (CRP), urine albumin to creatinine ratio (UACR), estimated glomerular filtration rate (eGFR), 24H ambulatory systolic and diastolic blood pressure (Amb. SBP, Amb. DBP), arterial stiffness measure pulse wave velocity (PWV), IPAQ long form continuous score MET-minutes/week (IPAQ), pre-first session resting SBP and DBP, maximum drop in supine SBP or DBP in the 55-110 minutes post-first heat or exercise session (Supine SBP or DBP drop), and total peripheral resistance (TPR), pulse wave velocity (PWV), renin, angiopoietin-2 (Ang2), endothelin-1 (Et1), and urine aldosterone.

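### Exploratory Aim 3, Model 3 puts the arm interaction on post-session BP but drops the arm-by-pre-session term, so a baseline-by-arm effect can pass for arm-specific prediction by the acute response

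*SAP*

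**What the plan says.** SAP section 4.1, Specific Aim 3, states: "We hypothesize that the reduction in blood pressure following acute stressors will be predictive of treatment effects on resting blood pressure". It adds: "These findings would provide significant predictive information beyond baseline resting blood pressures". Section 9.1 describes the purpose of the Aim 3 ANCOVAs in the same terms: "To test the association between acute decreases in blood pressure following an initial heat therapy session or exercise peak test" and the sustained reduction.

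Two of the three Aim 3 models matter here:

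- "Model 2, Post ambulatory BP ~ Pre-session BP + Intervention + Intervention\* Pre-session BP"
- "Model 3, Post ambulatory BP ~ Pre-session BP + Intervention + Post-session BP + Intervention\* Post-session BP"

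Pre-session BP is the mean of three readings before the first session. Post-session BP is a level: the lowest mean of three consecutive recovery readings. Section 9.1 also plans to display estimated means at chosen values of the interaction terms.

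Table 4 (section 5.5) lists acute-change variables as Aim 3 primary. The systolic one, Supine.SBP.1.ch, is defined as "Change from average pre-session resting SBP to Supine.SBP.low". None of the three Aim 3 formulas uses these variables. The acute change does appear elsewhere: section 9 plans Pearson correlations of acute with chronic change, and section 9.1 includes the supine drop in its exploratory correlations. No arm term or baseline adjustment is stated for those correlations.

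**The concern.** Aim 3 needs to separate two things: how the treatment effect varies with baseline pressure, and what the acute response adds to that. Model 2 allows the first. Model 3 is the only ANCOVA that contains the acute response, and it removes the term through which the first would be seen. Its interaction is on a level that itself contains the pre-session pressure.

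If the benefit of heat over exercise depends on baseline pressure, which the SAP examines in its own models, Model 3 can show an acute-response interaction when the fall carries no information. If the fall does predict in one arm only, the shared coefficient shrinks that signal. Models 2 and 3 are also not nested, so the gain beyond baseline cannot be read from comparing them.

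**Working it through.** The documents give no figure for Aim 3, so there is none to reproduce. The sample sizes are theirs: 50 enrolled and 40 completers (protocol section C; SAP section 6 gives the 50 and the 20% dropout). Every SD, correlation and slope below is an assumption, as is the two-sided 0.05 test of the interaction.

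**Step 1, algebra.** Let A be the arm and Change = Post − Pre. Then A × Post = A × Pre + A × Change. Model 3 gives both right-hand terms one coefficient.

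**Step 2, what that coefficient estimates.** Take 1:1 arms with equal covariances, and let k = ρ × SD(pre) / SD(post), the slope of pre-session on post-session BP.

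- A true arm-by-pre slope g with no effect of the fall gives an expected coefficient of g × k (truth 0).
- A true arm-by-change slope h with no baseline-by-arm effect gives h × (1 − k) (truth h).

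**Step 3, first simulation.** 4,000 runs; SD 10 mmHg for both readings (so k = ρ), residual SD 8, common pre-session slope 0.5, mean fall 8 mmHg in both arms. For g = 0.5 and an uninformative fall:

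| ρ | g × k | Simulated coefficient | False rejection, N=40 | N=50 |
|---|---|---|---|---|
| 0.5 | 0.25 | 0.25 | 14% | 16% |
| 0.7 | 0.35 | 0.34 | 22% | 29% |
| 0.8 | 0.40 | 0.40 | 30% | 37% |
| 0.9 | 0.45 | 0.45 | 35% | 45% |

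With A × Pre added, rejection is 4.6% to 5.7%. With neither effect present, Model 3 rejects at 4.6% to 5.6%. A true h = 1.0 is shrunk to 0.50, 0.30, 0.20 and 0.11 as ρ rises, against 1 − k = 0.5, 0.3, 0.2 and 0.1. If the fall predicts equally in both arms (true slope 0.50) and there is no baseline-by-arm effect, Model 3 returns 0.50.

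**Step 4, second simulation.** 2,500 runs, N=40. Underlying pressure has between-person SD 6 or 9 mmHg, pre-session noise has SD 4, the fall has SD 5 and is independent of level, and residual SD is 4.5. Here g is the change in the heat effect per mmHg of underlying pressure. Pre-intervention ambulatory BP is included as an extra covariate. With the fall uninformative and measured without error, Model 3's interaction rejects as follows:

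| Between-person SD | g = 0 | 0.2 | 0.3 | 0.5 |
|---|---|---|---|---|
| 6 | 5% | 7% | 10% | 21% |
| 9 | 5% | 13% | 24% | 54% |

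Hand check at SD 9, g = 0.5: the spurious coefficient should be 0.5 × 81 / (81 + 16 + 25) = 0.33 in size. It should be split as about 0.17 in opposite directions between the arms, and the simulation gives +0.17 in exercise and −0.17 in heat.

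Re-running with and without the ambulatory covariate, and with the post-session reading given its own independent SD 4 noise, widens the ranges to about 10-27% at g = 0.3 and 19-55% at g = 0.5.

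**Step 5, what the extra term buys.** When the fall is measured without error, the corrected model rejects at 4-6%. With independent noise it rejects at about 7-9% at g = 0.5, because a noisy pre-session value leaves some baseline information in the change. Power for a fall that predicts in the heat arm only (0.8 mmHg per mmHg), with no baseline-by-arm effect:

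| Noise in the post-session reading | SD | Model 3 | Corrected |
|---|---|---|---|
| Same as pre-session (fall error-free) | 9 | 17% | 60% |
| Independent | 9 | 16% | 31% |
| Independent | 6 | 23% | 33% |

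**The case against.** The strongest reply is that the aim is prediction, not a between-arm difference in prediction. It is labelled exploratory, section 7.5 disclaims multiplicity control, and no decision rule is attached to Model 3. The artefact also needs a real baseline-by-arm effect, which Model 2 would show. All of this is fair and keeps the point small. It does not answer it: Model 3 itself contains the arm interaction, the SAP plans to display means from it, and seeing a baseline effect in Model 2 does not remove it from Model 3.

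Three stronger readings are tempting, and the documents do not support them.

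- A reader might infer that entering the level instead of the fall is itself a mistake. As a main effect it is not. Pre-session BP is in the model, so the two parameterisations agree exactly (coefficient 0.7995 either way in one simulated data set, with the same p value).
- A reader might infer that the SAP never analyses the fall directly. It does, through the correlations in sections 9 and 9.1. As described, these carry no arm term or baseline adjustment, so they do not repair Model 3.
- A reader might infer that the extra term raises power from 17% to 60%. That is a best case, in which the fall is measured without error.

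**Conclusion.** The point holds as a low-severity fault of specification. Model 3's interaction mixes baseline-by-arm with change-by-arm effects, against the stated purpose of predicting beyond baseline pressure. How much this matters depends on quantities the documents do not give. It is nil for false rejection if there is no baseline-by-arm effect, about 10-27% at an assumed slope of 0.3, and 19-55% at 0.5. Dilution of a true arm-specific effect does not need a baseline-by-arm effect: at SD 9, with the fall measured without error, a heat-arm slope of 0.8 is estimated at 0.49, and an exercise-arm slope of 0.32 appears where the truth is 0. Nothing here touches the trial's primary comparison, and it does not show that Aim 3 will give a false result, only that Model 3 could not tell the two explanations apart.

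**What to change.** In SAP section 9.1, rewrite Model 3 as:

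`Post ambulatory BP ~ Pre-session BP + Intervention + Intervention*Pre-session BP + Post-session BP + Intervention*Post-session BP`

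Model 3 then contains Model 2, and the gain beyond baseline is a direct comparison of the two. Report the acute-response slope in each arm and their difference, with 95% confidence intervals.

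Once the added term is present, entering the change (post-session minus pre-session) in place of post-session BP gives the same interaction estimate and p value, and is easier to read. If that form is chosen, compute the diastolic change from diastolic readings. Table 4 defines Supine.DBP.1.ch against Supine.SBP.low, and that entry must be corrected first.

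The cost is one degree of freedom and a wording change, with no new data. The text should note that noise in the pre-session readings can leave some residual confounding with baseline, and that the power gain may be only small to moderate. It should also say how the planned correlations of acute and chronic change are to be read beside Model 3.

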In Protocol 2 exploratory analyses, the relationship between outcomes and the highly related covariates/potential confounders listed in **Table 5** at baseline and over time will be characterized through Pearson or Spearman correlations as appropriate based on distributions of data. Clustering of individuals and variables will be characterized through principal component analyses and unsupervised hierarchical clustering. Variables will be centered and scaled prior to principal component analysis. Additional exploratory correlations and PCA were then subsequently performed among the following Project 1 and 2 variables: age, body mass index (BMI), HbA1c, total cholesterol (TC), Interleukin-6 (IL-6), C-reactive Protein (CRP), 24H ambulatory systolic and diastolic blood pressure (Amb. SBP, Amb. DBP), IPAQ long form continuous score MET-minutes/week (IPAQ), pre-first session resting SBP and DBP, mean perfusion calibration of gray matter (Pcalib. GM) and white matter (Pcalib. WM), white matter hyperintensity (WMH) mean and volume, and mean arrival time in gray matter (Arr. Time GM) or white matter (Arr. Time WM), cognitive measure mini-mental state exam (MMSE, measured at pre-intervention only), list age-corrected sorting score and age-corrected picture sequence score, memory domain composite score (memory score, average z-scores of list age-corrected sorting score and age-corrected picture sequence score) and brain biomarkers of ADRD risk, whole hippocampus, right and left entorhinal cortex normalized to estimated total intracranial volume (LERC/eTIV, RERC/eTIV).

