velocity measure of arterial stiffness across timepoints by mixed effect model

Figure 6. Biomarkers of inflammation and oxidative stress in heat therapy or exercise training intervention groups at each study timepoint.

Supplementary Table 3. Estimated effects of heat therapy compared to exercise training on biomarkers of inflammation and oxidative stress across timepoints by mixed effect  
05/17/2024: Additional exploratory correlation and PCA analyses were added to the analysis plan with subsets of Project 1 and Project 2 variables.

## Protocol 2

Figure 7. Volume of hippocampus by region and estimated Total Intracranial Volume (eTIV) by intervention group at pre- and post-intervention.

Figure 8. Cognitive measures by heat therapy or exercise training intervention group.

Table 4. Cognitive and brain biomarker outcomes by group and timepoint

Table 5. Cognitive and brain biomarker outcome associations with blood pressure and arterial stiffness

Supplementary Figure 5. Correlations between cognitive measures and brain biomarkers of ADRD-risk

Supplementary Figure 6. Principal component analysis plot showing the multivariate variation among participants in terms of cognitive measures and brain biomarkers of ADRD risk

Supplementary Figure 7. Hierarchical clustering of cognitive measures and brain biomarkers of ADRD risk

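### The joint Project 1 and 2 exploratory PCA and correlations enter the memory composite beside the two scores it averages, which inflates one component by construction; separately, the Project 1 list names PWV twice.

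*SAP*

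**What the plan says.** SAP 9.1 describes three sets of exploratory multivariate analyses, which should be kept apart.

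- **Project 1 set (correlations and PCA).** The variable list names pulse wave velocity in two places: "arterial stiffness measure pulse wave velocity (PWV), IPAQ long form continuous score" and later "total peripheral resistance (TPR), pulse wave velocity (PWV), renin, angiopoietin-2 (Ang2").
- **First Protocol 2 set (correlations, PCA and hierarchical clustering).** This covers the outcomes and the covariates of Table 5. Neither Table 1 nor Table 5 lists the two component memory scores as separate variables. The scaling rule is stated here: "Variables will be centered and scaled prior to principal component analysis".
- **Joint Project 1 and 2 set (correlations and PCA, no clustering named).** The list includes "list age-corrected sorting score and age-corrected picture sequence score, memory domain composite score (memory score, average z-scores of list age-corrected sorting score", and the composite's own entry reads in full "memory domain composite score (memory score, average z-scores of list age-corrected sorting score and age-corrected picture sequence score"), so both component scores and their composite are separate entries.

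SAP 5.5, Table 4 defines the composite as "Averaged z-scores (centered & divided by standard deviation) of age-corrected picture sequence score (age_cor_score") and the age-corrected list-sorting score. SAP 9.1 gives no rule for dropping derived or repeated variables.

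**The concern.** A PCA on scaled variables gives each entry one unit of variance and looks for directions that many entries share. A variable that is the average of two others in the same set adds no information but does add a unit of variance along a direction already present. Two things follow whatever the data show. The composite will correlate strongly with each of its parts, and one component will carry more variance than the measured data support.

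The SAP describes the study as focused on learning and hypothesis generation, without control for multiple comparisons (SAP 7.5). Correlation and PCA displays are one route by which such hypotheses arise. A grouping of memory variables in the joint PCA, or a row of strong memory correlations, could be read as a finding when part of it comes from the way the set was assembled.

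**Working it through.** The SAP gives no figure for these analyses, so there is none to reproduce.

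**Inputs from the documents**
- Joint list: 24 entries by count, 3 of them memory (two scores and the composite); 23 without the composite.
- The same list holds four blood pressure measures (24-hour ambulatory SBP and DBP, pre-first-session SBP and DBP), two perfusion, two arrival-time, two white matter hyperintensity and three hippocampal or entorhinal measures.
- Protocol 2 enrols at most 40 (Protocol, Protocol 2 methods).
- Project 1 list: 22 entries by count, 21 distinct.

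**Assumed, because the documents do not give them**
- Correlation r between the two memory scores: 0 and 0.3.
- n = 40, and n = 32 (40 less 20% dropout, borrowing the Protocol 1 allowance: 40 × 0.8 = 32).
- Correlations among the other variables: none; or blood pressure at 0.4 or 0.6 with further blocks (perfusion pair 0.7, arrival-time pair 0.7, hyperintensity pair 0.5, hippocampal and entorhinal 0.4).
- The z-scores are standardised in the same sample that enters the PCA.

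**Step 1. Composite-part correlation.** Let c = (z1 + z2)/2 with corr(z1, z2) = r. Then cov(c, z1) = (1 + r)/2 and var(c) = (1 + r)/2, so corr(c, z1) = √((1 + r)/2).
- r = 0: √0.5 = 0.71
- r = 0.3: √0.65 = 0.81

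**Step 2. Eigenvalues of the memory block.** The difference z1 − z2 gives eigenvalue 1 − r with or without c. The sum direction has variance 1 + r and correlates exactly 1 with c. Together they form a 2 × 2 block with trace (1 + r) + 1 and determinant 0, so its eigenvalues are 2 + r and 0. Without c, the sum direction has 1 + r.
- r = 0: 2.0 instead of 1.0
- r = 0.3: 2.3 instead of 1.3

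The zero eigenvalue holds whatever the other variables do. The full unit goes to this one component if memory is uncorrelated with the rest.

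**Step 3. Does that component lead?** Four blood pressure measures with common correlation ρ have a leading eigenvalue of 1 + 3ρ: 2.2 at ρ = 0.4 and 2.8 at ρ = 0.6. The inflated memory eigenvalue (2.0 to 2.3) straddles the first value and lies below the second. The uninflated one (1.0 to 1.3) lies below both. The crossover 2 + r = 1 + 3ρ is at ρ = (1 + r)/3, which is 0.33 for r = 0 and 0.43 for r = 0.3.

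**Step 4. Simulation at the trial's size.** The measure is the share of simulated datasets in which a memory variable has the largest absolute loading on the first component (n = 32 and 40, r = 0 and 0.3).

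| Other variables | With the composite |
|---|---|
| All independent | about 74–97% |
| Blood pressure at 0.4, other blocks as above | about 28–52% |
| Blood pressure at 0.6, other blocks as above | about 5–25% |

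Without the composite the share is 0–19% across these settings; the upper end belongs to the independent case. With blood pressure at 0.6, first-component scores with and without the composite correlate at 0.97–0.99, so the first component itself hardly changes.

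**Step 5. PWV.** A column entered twice gives eigenvalues 2 and 0 in place of a single 1. That applies only if the repeat in the text was carried into the data. If it was, PWV holds more than half of the first component's squared loading in 28% (n = 40) to 58% (n = 50) of datasets when all else is independent. The share is 0–0.2% when the four blood pressure measures correlate at 0.6.

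**The case against.** The strongest reply has four parts.

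1. **The first component may be untouched.** The list contains several groups that measure nearly the same thing, and SAP 9.1 itself calls the Protocol 2 covariates highly related. Independence of all other variables is therefore not a realistic setting, and the 74–97% range should not be taken as the expected effect. This stands. A reader might infer that the leading axis of the PCA will be a memory artefact; the documents do not support that, because they give no correlations and a moderately correlated blood pressure block would usually lead.
2. **Clustering and the planned figures are not shown to be affected.** Clustering is named only for the first Protocol 2 set, whose tables do not list the component scores. Supplementary Figure 6 is captioned "Principal component analysis plot showing the multivariate variation among participants in terms of cognitive measures and brain biomarkers of ADRD risk", which fits that first set better than the joint list with its age, lipid, inflammation and blood pressure variables. This stands too, although neither caption says which cognitive measures are used.
3. **PWV is probably a listing repeat.** Table 4 defines one PWV variable, and naming it twice in prose does not show that it was entered twice. The repeat is also in a different PCA from the memory composite, so the two do not act on one component.
4. **It is exploratory, and the composite's definition is printed in the list.** A careful reader can see that composite-part correlations are built in. This is fair for the correlation matrix and limits the importance of the point. It helps less with a PCA, where the extra unit of variance is not visible in the plot.

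None of these parts disputes that all three memory entries are in the joint PCA, or the algebra in steps 1 and 2.

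**Conclusion.** The point holds for the joint Project 1 and 2 correlations and PCA. Followed as written, the text produces composite-part correlations of √((1 + r)/2), a memory-block eigenvalue of 2 + r rather than 1 + r, and one zero eigenvalue. The first and third of these need only the composite's definition and common standardisation. The second also takes memory as uncorrelated with the other variables.

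The effect on the leading component is conditional. The simulated share ranges from about 5% to 97% over the assumed correlations, against 0–19% without the composite, and the documents cannot narrow it. Where blood pressure leads, the inflation falls on a later component.

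Two stronger readings are not supported: that the clustering and Supplementary Figures 6 and 7 contain the artefact, and that PWV was analysed twice. Both are questions for the analyst to confirm.

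Materiality is low. No component score feeds a test, an endpoint or the sample size, and the planned regression on the memory composite is unaffected.

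**What to change.** In SAP 9.1:

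- In the joint Project 1 and 2 PCA, enter either the memory composite or its two component scores, not both. Dropping the composite takes the list from 24 to 23 entries and removes the forced zero eigenvalue.
- If the correlation matrix still shows all three, state that the composite-part correlations are built in and do not report them as findings.
- State which cognitive measures enter the first Protocol 2 PCA, the clustering and Supplementary Figures 6 and 7. If the component scores are used there, apply the same rule.
- In the Project 1 list, delete the second mention of PWV ("total peripheral resistance (TPR), pulse wave velocity (PWV), renin") and confirm that the variable is entered once.

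The cost is a wording edit and a re-run of the exploratory plots. No data collection, primary or secondary analysis, or sample size changes.
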